# 4.3 Subject Recruitment, Enrollment, and Screening

Recruitment will be of patients who are residents of nursing homes who have proven CoV infection. Subject recruitment will be by medical, nursing, and other nursing home staff and/or research staff. Permission will be obtained from each location before recruitment begins.

Trained clinical coordinators will contact patients, health care proxies (as appropriate), and responsible nursing home staff (including the attending physicians, nurse-practitioners, or physician's assistants) and assist in recruitment and carry-through of the protocol. For each nursing home, during discussions leading to participation with their administrators and medical and nursing leadership, a key contact will be identified who will ensure access, consent, data and sample collection, and data integrity and identify and assist in resolving issues as the study proceeds. In most cases, this will be the Medical or Nursing Director or their designees. Written and informed consent will be obtained by appropriately trained study personnel with support from the nursing home staff as needed. In the pandemic situation where access to nursing homes and hospitals is limited, if allowed, digital/electronic consent can be obtained from the patient's LAR and must be documented by the investigator or the authorized designee (see Section 6.1). Documentation of recruitment and enrollment efforts will be maintained in a secure institutionally-supported database. Clinical judgment regarding inclusion and exclusion will be *per* the study physicians and/ or the patient's physicians, nurse-practitioners, or physician's assistants.

### 4.4 Early Withdrawal of Subjects

# When and How to Withdraw Subjects

All subjects will be assessed during the initial day of medication administration, subsequent days of medication administration, and all study visits. If a severe adverse event (SAE) occurs at any time during administration of the drug regimen, a formal review will occur. If 4 or more events accrue, the pilot study will be held and either the dosing regimen revised or discontinuation of the study protocol will occur. Other interventions will be as *per* the direction of the Food and Drug Administration (FDA), Mayo Clinic Institutional Review Board (IRB), and policies of the patient's nursing home.

### **4.4.1.** Study Completion:

For each subject in the study, the end of study will be reached when treatment and post-treatment safety follow-up periods have been completed, including follow-up of patients discharged from the nursing home to home, other care settings, or hospital, *i.e.* subjects will be followed if

feasible, irrespective of their location, by telephone or in person until the 180 ( $\pm$ 14) day follow-up visit or death.

### **4.4.2.** Treatment Discontinuation:

A subject's treatment may be discontinued prior to that subject completing the 4 days of drug treatment. Subjects whose treatment has been discontinued will remain in the study and, if feasible, will continue to be assessed for all planned efficacy and safety endpoints and will be included in statistical analyses. Some reasons may include:

- Subject safety issues
- Failure of subject or staff to adhere to protocol requirements
- Subject voluntarily withdraws from treatment
- Subject is unable to tolerate continued IP administration
- Subject experiences a Grade 3 or higher adverse event attributed to the IP by the investigator
- Subject experiences a Grade 3 or higher clinically significant laboratory abnormality attributed to the IP by the investigator
- Treating physician determines that continuing study treatment would not be in the subject's best interest
- Subject becomes lost to follow-up
- The investigator or the subject's nursing home attending physician, physician's assistant, or nurse-practitioner may discontinue a subject's treatment (without regard to the subject's or their LAR's consent) if they believe that continued treatment would be contrary to the best interests of the patient.

If premature treatment discontinuation occurs for any reason, the reason for premature treatment discontinuation, along with who made the decision (subject, LAR, responsible nursing home physician, physician's assistant, nurse-practitioner, investigator) will be recorded in the CRF.

# 4.4.3. Subject Withdrawal:

A subject may be withdrawn from the study prior to that subject's completing all of the study related procedures if the subject or LAR decides to withdraw from the study (withdrawal of consent). Withdrawn subjects may not reenter the study.

# 4.4.4. Premature Withdrawal from Study:

Subjects or their LAR may voluntarily withdraw from the study for any reason at any time. Subjects are considered withdrawn if they or their LAR state an intention to withdraw further participation in all components of the study or if subjects die. If premature withdrawal occurs for any reason, the reason for premature withdrawal from the study, along with who made the decision (subject, LAR, responsible nursing home physician, physician's assistant, or nurse-practitioner, investigator) will be recorded in the CRF.

### 4.4.5. Reporting of Serious Adverse Events and Unanticipated Problems:

When an adverse event has been identified, the study team will take appropriate action necessary to protect the study subject and then complete the Study Adverse Event Worksheet and log. The investigator will evaluate the event and determine necessary follow-up and reporting required.

### 4.4.6. Subject Replacement:

Subjects withdrawn (due to withdrawal of consent) from the study will not be replaced and analytic methods will be by intent-to-treat.

### 4.5. Data Collection and Follow-Up for Withdrawn Subjects

- For withdrawn subjects (due to withdrawal of consent) not undergoing any study intervention, no additional follow-up will be done.
- For withdrawn subjects (due to withdrawal of consent) receiving Fisetin (Intervention), any additional evaluation will be for subject safety only. Research data will not be collected on subjects after withdrawal of consent.

# 5. Investigational Product (IP)

# 5.1. Description

While Fisetin is currently widely available and marketed as a dietary supplement at daily doses of 100 mg or more, this study will use a product manufactured under GMP conditions. The Fisetin will be supplied in 100 mg capsules or powder dissolved in water, apple sauce, pudding, yogurt, or enteral hydration/ nutrition solutions to be administered orally or enterally (NG or D tube). The investigational supplies will be obtained from Vital Nutrients, a contracted GMP manufacturer. Fisetin capsules supplied by Vital Nutrients are size #3 or 00 opaque blue in color.

Current inventory lot (20E44) of Fisetin capsules from manufacturer Vital Nutrients were tested by the ICL using mass spectroscopy. The sample results lead us to believe that all of the active capsules contain Fisetin active ingredient. The placebo comparator used for this study was manufactured using the same size opaque blue capsules by Vital Nutrients or cellulose powder with food dye to approximate the appearance of Fisetin/ cellulose powder as closely as possible. Each placebo capsule is mainly composed of cellulose along with some coloring agents to approximate the appearance of the active capsule contents. None of the current inventory lot (20E44) of the placebo capsules contained Fisetin that exceeded the acceptance criterion (≤2 mg Fisetin *per* capsule).

# 5.2. Treatment Regimen

### 5.2.1. Fisetin/Placebo

The treatment dosing regimen is based on the preclinical information available about Fisetin along with information about similar clinical drug trials using the alternative senolytic compounds D and Q. Participants will be administered Fisetin over two 2-day courses of treatment during the study duration. On study each of Days 0 and 1 and Days 8 and 9, subjects will receive a target dose of 20 mg/kg of body weight. Therefore for an adult with a body weight of 75 kg, on each day the participant will take 15 of the 100 mg capsules or an equivalent amount of Fisetin powder mixed with water, other room temperature or chilled drinks, foods such as apple sauce or pudding, or in enteral solutions, at room temperature or chilled. Dosing should be completed in as short of a time as possible, with a goal of 30 minutes to complete ingestion of the capsules.

Dosing will be done during 2 sets of 2-day oral or NG or D tube treatments with Fisetin (~20 mg/kg/day for 2 consecutive days) on Days 0 and 1 and Days 8 and 9.

There are no recommended dosing adjustments for kidney or liver dysfunction. For identified drug-drug interactions, subjects will either be excluded from the study or drug modifications will be requested.

# 5.2.2. Concomitant Therapies

"Concomitant therapies" refers to treatment that subjects receive during the conduct of the study. All concurrent therapies, including medications, intubation, and oxygen will be recorded.

### 5.2.3. Standard of Care

Subjects will continue to receive institutional standard of care for the treatment of COVID-19 pneumonia and other conditions. The use glucocorticoids, Hydroxychloroquine, Azithromycin, Remdesivir, or Metformin is permitted. Subjects administered Rapamycin or other mTOR inhibitors, should they become standard of care, will be withdrawn unless the Rapamycin or other mTOR inhibitors are held for ≥5 days before the first dose of Fisetin on Day 0 until 1 hour after the final Fisetin dose on Day 9. Subjects started on other treatments for COVID-19 will continue to be followed if possible until the end of the study.

# 5.3 Method for Assigning Subjects to Treatment Groups

Subjects will be randomized to either Fisetin or placebo using an internet-based, web browser randomization procedure maintained by the data management team at Wake Forest School of Medicine. Study coordinators access the randomization application through the trial website. Access to this application is password-protected and its communications are encrypted. Once security requirements are satisfied, consent and eligibility of the participant are verified, and randomization will occur. Randomization is controlled centrally based on each potential participant's consent and eligibility status. ONLY eligible participants will have the randomization button displayed. It will be impossible to randomize an ineligible person, or a person for whom screening or consent is incomplete. We will use a permuted block randomization scheme with varying block sizes and without stratification so that group assignment is balanced as the study proceeds, but study personnel will not be able to predict treatment assignment.

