# **Study Summary**

Title	COVID-FIS: A Phase 2 Placebo-Controlled Pilot Study in COVID-19 of Fisetin to Alleviate Dysfunction and Excessive Inflammatory Response in Older Adults in Nursing Homes	
Running Title	COVID-FIS: COVID-19 Pilot Study of Fisetin to Alleviate Dysfunction and Inflammation	
Protocol Number	20-008867	
Phase	Phase II	
Methodology	Randomized, placebo-controlled, double-blind secondary prevention trial	
Overall Study Duration	32 months	
Subject Participation Duration	Subject participation duration 6 months (screening, 4 days treatment, follow-up visits, unblinded at the end of the study)	
Single or Multi-Site	Multi-Site	
Objectives	
 
To prevent COVID-19 (CoV) disease complications by a 7 point score adapted from the WHO Ordinal Scale for Clinical Improvement of CoV (Appendix 1)
 
To evaluate safety and tolerability of Fisetin in this patient population
 
To reduce progression of severity of SARS-CoV-2 infections with no, mild, or moderate to severe or critical symptoms. To decrease senescent cells, inflammation, and physical dysfunction (frailty)
 
	
Number of Subjects	250 enrolled and screened, 150 accrued and randomized	
Diagnosis and Main Inclusion Criteria	Women or men age $\geq$ 65 years in a nursing home with mRNA-PCR test-proven CoV infection. SpO2 $\geq$ 85% (on room air or $\leq$ 2 L of supplemental oxygen) at time of enrollment.	
Study Product, Dose, Route, Regimen	This study will involve a 2-day oral or NG or D tube course of Fisetin twice (~20 mg/kg/day for 2 consecutive days; Days 0, 1, 8 and 9).	
Duration of Administration	4 out of 10 days	
Reference therapy	Reference therapy Placebo-controlled	
Statistical Methodology	Assuming 75 subjects/ group with a significance level of 0.05, the study will have 80% power to detect an odds ratio of 2.24 comparing the placebo- to Fisetin-treated group, using the 7-point severity score at Day 14 as the endpoint in an ordinal logistic regression model.	

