## 3 Study Design

#### 3.1 General Description

This study is a pilot, randomized, placebo-controlled, multi-site study of Fisetin in elderly nursing home participants. A total of 250 participants will be enrolled in this study. Study staff and participants will be blinded with regards to groups. Subjects will be randomized to placebo or treatment. Fisetin 20 mg/kg/day or placebo will be made available by the study staff for oral or enteral administration on study Days 0, 1, 8, and 9.

If Remdesivir or another anti-viral agent or immunization should become standard of care in nursing home CoV patients (*e.g.*, approved by the FDA) during the study, patients being treated with such agents may be enrolled, with randomization stratified based on whether subjects are on such an anti-viral agent. We conducted studies of mice (N=6 old mice; age 22.9±0.7 months [means±SEM]; females) on higher doses of Fisetin than to be administered here (100 mg/ kg/ day for 2 days) by gavage and Remdesivir (50 mg/ kg/ day) i.p. We did not find Fisetin plus Remdesivir resulted in increased toxicity (changed body weight, food intake, activity, grooming, appearance, or frailty score) during any of the 4 days following administration *vs.* Remdesivir alone (Table 3; 100 mg/ kg/ day for 2 days by gavage; N=6 old mice; age 23.4±0.7 months). Therefore, if patients already in COVID-FIS are started on Remdesivir, they will not be withdrawn from the study. During statistical analyses, patients will be analyzed regarding Remdesivir administration *post hoc.* 

Table 3. Remdesivir + Fisetin is Not More Toxic than Remdesivir Alone

Treatment	Age (Mo.)	Frailty Score	Body Wt. (g)	Body Temp. (°C)	Body Wt. (g)	Frailty Score	Body Wt. (g)	Body Temp. (°C)	Body Wt. (g)
Date	5/4	5/4	5/4	5/4	5/9	5/10	5/10	5/10	5/11
RDV+Fisetin	25.03	0.357	27.2	31	26.00	0.37	25.7	31.73	26.1
RDV+Fisetin	22.20	0.125	34.2	32	34.9	0.185	33.8	32.07	34.1
RDV+Fisetin	22.35	0.143	30.1	32	28.5	0.259	27.6	32.83	28.2
RDV+Fisetin	19.47	0.21	29.5	32	27.3	0.278	27.6	31.9	27.8
RDV+Fisetin	24.18	0.20	42.2	32	41.5	0.204	39.8	30.9	39.7
RDV+Fisetin	24.18	0.161	28.3	31.7	27.9	0.204	27.9	32.17	28.3
Mean	22.90	0.2	31.9	32	31.02	0.25	30.4	31.93	30.7
SEM	0.752	0.031	2.08	0.14	2.24	0.026	2.00	0.24	1.93
RDV	24.01	0.214	27.6	31.7	27.1	0.241	26.6	31.67	26.8
RDV	23.59	0.232	27.9	32.1	27.9	0.296	27.8	32.6	28
RDV	22.20	0.268	30.9	31.6	29.9	0.241	29.1	32.3	29.3
RDV	22.20	0.125	34.5	32.4	34.1	0.185	33.8	32.77	33.5

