# 3.3 Duration of Participation

The study is estimated to complete enrollment within 18 months from study initiation; however, enrollment will remain open until the study goal is met. The duration of this study for each subject will be a maximum of 6 months. Study treatment will take approximately 4 out of 10 days. Subjects will be followed for up to 6 months or death, whichever comes first, including any available laboratory and chest imaging results if done as part of nursing home care. This will be done through study staff and health care providers in the nursing home or, if transferred to hospital, another facility, or home, by study staff contacting patients, their LAR, and/or their health care providers daily if feasible from Days 0 to 14 and at Days 30, 90 and 180 ( $\pm 14$ ; unblinding) after Fisetin vs. placebo was commenced if feasible, or from nursing home or hospital records. Adverse event reporting will be collected daily if feasible from the time of consent through Day 14. Adverse events will be assessed again at Days 30, 90 and 180, if possible. Subjects will not be required to return to the nursing home if discharged home or to another care setting.

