# 8 Statistical Plan

### 8.1 Sample Size Determination

Power calculations for the comparison of the Fisetin and control groups were made assuming an equal distribution among the 7-point scale categories at Day 14 among the controls using a two-sided significance level of 0.05 (alpha). With 75 subjects per group, the study would have 80% power to detect a log odd's ratio of 0.81 which translates to an odd's ratio of 2.25 comparing the control to Fisetin group. Power calculations were run using the PASS software package.

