#### 8.2 Statistical Methods

All participants who are randomized will be included in the primary efficacy analysis. The analysis will follow the ITT principle (*i.e.* according to the treatment arm they are randomized to). For the primary analysis using the values of the 7-point scale, we will test the coefficient of the treatment effect (as a fixed effect) in an ordinal logistic regression model using a 2-sided 0.05 level Wald test after adjusting for key baseline variables such as baseline COVID severity status, age, and sex that show imbalance between the groups. Subjects who withdraw early but received at least some treatment will have their last known values carried forward until they complete the study at Day 180±14. All participants who receive any dose of drug (Fisetin or placebo) will be included in the safety and tolerability evaluation. The definitions of adverse events are described in Sections 9.1-9.3. Participants will be assessed over the entire period of drug administration. Frequency tables will be generated to summarize the occurrence of AE's by treatment arm. Comparisons of the rates of individual AEs will be done using tests of proportions such as the Fisher's exact test or Chi-squared test.

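### The 8.2 rule of adjusting only for imbalanced variables would leave out date of randomisation; naming it in advance is a cheap gain if outcomes drift strongly during enrolment

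*Combined protocol and SAP*

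**What the plan says.** - **Allocation (5.3).** Central randomisation by a "permuted block randomization scheme with varying block sizes and without stratification so that group assignment is balanced as the study proceeds". Block sizes are not given.
- **Enrolment (3.3 and Study Summary).** Estimated at 18 months, but "enrollment will remain open until the study goal is met". The whole study is put at 32 months.
- **Changing care (3.1).** The protocol provides for the case that Remdesivir or "another anti-viral agent or immunization should become standard of care in nursing home CoV patients". It would then stratify randomisation by antiviral use, and it plans a post hoc look at Remdesivir.
- **Primary analysis (8.2).** "we will test the coefficient of the treatment effect (as a fixed effect) in an ordinal logistic regression model", with a two-sided 0.05 Wald test. Adjustment is for key baseline variables, with severity, age and sex as examples, and only for those that differ between the arms. Date of randomisation, calendar period and block are named in no analysis in section 8.
- **Power (8.1).** "With 75 subjects per group, the study would have 80% power to detect a log odd's ratio of 0.81", "assuming an equal distribution among the 7-point scale categories at Day 14 among the controls". There is one control distribution, with no time component. The Study Summary gives "80% power to detect an odds ratio of 2.24", a rounding difference.

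**The concern.** Sections 5.3 and 8.2 pull against each other. Blocking holds the arms level over enrolment order. If the largest block were 6, for example, the arms could never differ by more than 3 at any point. A covariate rule triggered by observed imbalance will therefore almost never bring in date of randomisation, even if date turns out to be one of the stronger predictors of outcome. That could happen in a COVID-19 trial with open-ended enrolment and treatment and immunization changing meanwhile.

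Two things follow if outcomes drift. The model-based standard error of the unadjusted treatment coefficient takes no account of the blocking, so it overstates that estimator's true spread and the Wald test becomes conservative. The unadjusted test also forgoes the power that any prognostic covariate brings. The trial has little reserve to absorb this: its size sits almost exactly at 80% power.

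**Working it through.** **1. The plan's own figure.** Inputs from 8.1: two-sided alpha 0.05, 75 per arm (N = 150), log OR 0.81, controls 1/7 in each of 7 categories. The proportional-odds sample-size formula is

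N = 12 (z₁₋α/₂ + z₁₋β)² / [(log OR)² (1 − Σ p̄³)],

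where p̄ is the category proportion averaged over the arms. The numerator is 12 × (1.960 + 0.842)² ≈ 94.2, and 1 − Σ p̄³ ≈ 0.976. So N ≈ 94.2 / (0.6561 × 0.976) ≈ 147. At N = 150 power is 80.8% for log OR 0.81 and 80.4% for OR 2.24. The stated 80% is reproduced.

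**2. Adding drift.** The documents give no drift figure, so its size is an assumption, expressed as the odds ratio for outcome between the first and last participant. The simulation used:
- 5,000 trials per scenario, 150 participants each, blocks of 2, 4 and 6 (assumed);
- linear drift in the log odds over enrolment order, with the pooled control distribution held uniform over 7 categories;
- a proportional-odds fit with Wald test, without and with a linear enrolment-time term;
- treatment log OR 0.81, conditional on time, for power, and 0 for type I error.

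| Drift | Power without / with date | Type I error without / with date | Null, without date: model SE / true SD |
|---|---|---|---|
| none | 80.7% / 80.8% | 4.7% / 4.8% | 0.287 / 0.290 |
| 2-fold | 79.5% / 80.3% | 5.3% / 5.6% | 0.287 / 0.292 |
| 4-fold | 77.7% / 80.4% | 5.1% / 5.7% | 0.287 / 0.285 |
| 8-fold | 76.6% / 80.7% | 3.5% / 4.8% | 0.287 / 0.272 |
| 16-fold | 71.4% / 79.3% | 3.1% / 5.2% | 0.287 / 0.266 |

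Monte Carlo error on the type I figures is about √(0.05 × 0.95 / 5000) = 0.3 points. A separate 3,000-run simulation at 16-fold gave type I error 3.5% without date, and power 73.5% without against 80.8% with. Another, with 3,000 null runs at 4-fold, gave 4.2% without and 4.9% with.

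**3. Where the conservatism comes from.** With an SE larger than the true SD, the effective critical value is 1.96 × SE/SD. At 8-fold it is 1.96 × 0.287/0.272 ≈ 2.07, or about 3.9% two-sided. At 16-fold it is 1.96 × 0.287/0.266 ≈ 2.11, or about 3.4%. Both agree with the simulated rates within about one or two Monte Carlo errors. With unblocked 75:75 allocation and 16-fold drift, SE and SD agree (0.287 against 0.292) and type I error is 5.5%. The conservatism is therefore due to blocking.

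**4. Where the power gain comes from.** At 16-fold drift, adding date moves the mean coefficient from 0.72 to 0.82, while its SE rises slightly, from 0.293 to 0.297. The ratio goes from 0.72/0.293 ≈ 2.5 to 0.82/0.297 ≈ 2.8. The gain is a less attenuated odds ratio (non-collapsibility), not a narrower interval. Without blocking it is just as large: 70.6% against 79.4% at 16-fold, and 76.7% against 79.5% at 4-fold.

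**5. Is the range conceivable?** Sections 1.1 and 1.6 put mortality in infected nursing home residents at 25–50%, that is, odds of 0.33 to 1. If it fell to an assumed 10% (odds 0.111), the odds ratio would be 3 to 9. At an assumed 5% (odds 0.053) it would be about 6 to 19. These only illustrate scale. Nothing in the documents says that such a fall occurs within the enrolment window.

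**The case against.** **The planned power may not be lost at all.** Section 8.1 powers an overall two-group comparison, which reads naturally as a marginal effect. The simulation treats 0.81 as conditional on date, so at 16-fold drift the marginal effect shrinks to about 0.72, and the formula in step 1 gives about 71% for 0.72 with no drift problem. If the conditional effect is raised until the marginal effect is about 0.81, unadjusted power is 80.9% at 8-fold and 80.5% at 16-fold, against 85.1% and 86.5% adjusted. This stands. Adjustment still gains power, but a reader who infers that the 80% claim is wrong goes further than the documents allow.

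**Other stronger readings also fail.** One might infer that the confidence interval is too wide and that adjustment would narrow it. It would not (step 4). One might infer that blocking causes the power loss, or that the real type I error is below 5% whatever happens. The first is contradicted by the unblocked runs. The second needs drift nearer 8-fold than 4-fold.

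**The plan is not silent.** The covariate list in 8.2 is open-ended, and 3.1 offers stratification by antiviral use and a post hoc Remdesivir analysis. This is partial cover. An open list does not help when the entry rule is observed imbalance, and 5.3 says there is no stratification.

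**It is a pilot and the error is on the safe side.** True, and this limits the weight of the point. Only linear drift with a linear term was examined, so other shapes are untested.

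**Conclusion.** The point holds as a cheap improvement to the primary model, not as an error that invalidates the design. Under 5.3 and 8.2 together, date of randomisation would almost never enter the analysis.

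Given strong drift, the unadjusted test is conservative because of the blocking: type I error is about 3.5–4% at 8-fold and 3–3.5% at 16-fold, and near 5% at 4-fold or less. Against a date-adjusted test it gives up about 1, 2–3, 4 and 7–8 points of power at 2-, 4-, 8- and 16-fold, most of which is the usual return from a prognostic covariate. False positives are not a risk.

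These sizes rest on an assumed linear drift, assumed block sizes, and log OR 0.81 read as conditional on date. With little drift the choice hardly matters.

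**What to change.** In 8.2, name date of randomisation (days since the first randomisation, in one stated form such as linear) as a fixed covariate in the primary ordinal model, included regardless of observed imbalance. Justify it as a prognostic covariate over which allocation is balanced, and state that the treatment odds ratio is conditional on it. Fixing the form in advance removes an analyst's choice.

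The cost is about two sentences and one degree of freedom. The randomisation system already holds the date, so nothing new is collected. With no drift, power is unchanged (80.8% with the term, 80.7% without).

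Separately, reconcile 3.1, which would stratify randomisation by antiviral use, with 5.3, which excludes stratification. If a stratification factor is used, it should also enter the primary model.
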